#### 6.2.1. Revised Sample Size (incorporated June 2016)

Sample size calculations were repeated after the trial was underway to incorporate the following changes to assumptions that affect study power. These changes include the following:

- Facility enrollment did not begin until just prior to participant enrollment rather than being carried out and completed during the 12 months prior to participant enrollment. As a result the duration of participant enrollment increased from 1 year to 3 years. The duration of the trial was increased to 4.5 years to maintain a median follow-up of 2.5 years.
- 2) A total of 266 rather than 402 facilities agreed to participate and 10 facilities withdrew from the trial after randomization resulting in a smaller number of clusters and larger size of clusters.
- 3) The percentage of participants who were lost to follow-up because of transplantation or facility transfer was higher than anticipated.

4) The observed intra-cluster correlation coefficient (ICC) for mortality determined during the trial after approximately 5000 participants were enrolled was lower than anticipated with observed ICC of approximately 0.01 rather than 0.03.

**Table 2R** shows sample size requirements under scenarios that incorporate the modifications described above including enrollment period of 36 months and a total study duration of 54 months, a cluster number of 256 and cluster size standard deviation (SD) of 10 or 16, a loss to follow-up rate of 10%, and an ICC for mortality of 0.012 or 0.015. For the primary analysis, the desired detectable hazard ratio for mortality risk is 0.85 comparing the Intervention arm to the Usual Care arm in the primary treatment assessment population. A sample size of 6,880 (4250 in primary analysis population) provides 77 – 82% power to detect a HR of 0.85 with a two-sided alpha of 0.05.

Enrollment Time/Total Study Time (mos)	# Clusters	SD for Cluster Size (1° Analysis Population)	Annual Loss to F/U	Annual Mortality Rate	ICC for Mortality	Sample Size for 1° Analysis Population	Total Sample Size	Power to detect HR 0.85
12/36	402	0	5%	18%	0.03	4020	6432	80%
36/54	256	10	10%	18%	0.015	4020	6432	78%
36/54	256	16	10%	18%	0.015	4020	6432	76%
36/54	256	10	10%	18%	0.012	4020	6432	80%
36/54	256	16	10%	18%	0.012	4020	6432	78%
36/54	256	10	10%	18%	0.015	4250	6800	80%
36/54	256	16	10%	18%	0.015	4250	6800	77%
36/54	256	10	10%	18%	0.012	4250	6800	82%
36/54	256	16	10%	18%	0.012	4250	6800	80%

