Protocol Summary	
Title	Time to Reduce Mortality in End-Stage Renal Disease (TiME) Trial
Short Title	TiME Trial
Protocol Number	817911
Sponsor	National Institutes of Health: NIDDK, Office of the Director
Design	Cluster-randomized, open label, pragmatic clinical trial
Principal Investigator	[name], M. D.
Objectives	
 
To determine whether dialysis facility implementation of a minimum hemodialysis session duration of 4.25 hours (versus usual care) for patients with end-stage renal disease initiating treatment with thrice weekly maintenance hemodialysis has benefits on mortality, hospitalizations and health-related quality of life.
 
To demonstrate the capacity to conduct a large, pragmatic clinical trial in partnership with two large dialysis provider organizations.
 

Intervention	Intervention facilities will recommend a minimum hemodialysis session duration of 4.25 hours. Control facilities ("Usual Care") will not implement a trial-driven recommendation about dialysis session duration.
Enrollment Period	3 years
Duration	4.5 years
Study Center(s)	Dialysis facilities operated by DaVita and Fresenius Medical Care, two large dialysis provider organizations
Data Coordinating Center	Clinical Research Computing Unit, Center for Clinical Epidemiology and Biostatistics, University of Pennsylvania Perelman School of Medicine
Number of Facilities & Patients	402 dialysis units
	6880 patients
Main Eligibility Criteria	Dialysis Facility Eligibility
	
 
Willingness of the facility's Medical Director, nephrologists and clinical leadership to adopt a facility approach of prescribing dialysis sessions of at least 4.25 hours for patients initiating treatment with maintenance hemodialysis (incident patients).
 

Protocol Summary	
	
 
Capacity to accommodate treatment session durations of at least 4.25 hours for incident patients.
 

	3. Facility use of the electronic data systems of the dialysis provider organization.
	Patient Eligibility
	Inclusion Criteria
	
 
Initiation of maintenance dialysis within the past 120 days.
 

	
 
Treatment with maintenance dialysis in a participating facility.
 

	
 
Age ≥18 years.
 

	Exclusion Criteria

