### 6.2. Sample Size

The sample size calculation is based on the comparison of mortality rates between the Intervention and Usual Care arms in the primary treatment assessment population (participants with body water volume ≤42L). The sample size requirements depend on the following factors: the minimum clinically important effect size, the mortality rate among incident patients (patients who have initiated dialysis within the past 120 days), the annual rate of loss to followup, type one error rate, and desired power. Since randomization for this trial will be at the level of the dialysis facility rather than at the patient level, the sample size also depends on the average number of participants enrolled within each dialysis facility and the intra-class correlation coefficient (ICC) (i.e., the correlation between two participants from the same dialysis facility, which describes the extent of similarity of mortality risk between two participants from the same dialysis facility).

Data from the two dialysis provider organizations from January 2011 to May 2012 suggests an overall mortality rate of 18% per year among incident patients. Other assumptions include a loss to follow-up rate of 5% per year. Loss to follow-up is expected to occur because of kidney transplantation, conversion from hemodialysis to peritoneal dialysis, and transfer to dialysis facilities belonging to a different dialysis provider organization. Based on data provided by both dialysis provider organizations, an ICC for mortality of 0.03 is expected. Based on the number of incident patients per facility at the two provider organizations, the average cluster size is expected to be 16, and it is expected that an average of approximately 10 (63%) of these patients will belong to the primary treatment assessment population.

**Table 2** shows sample size requirements under different scenarios based on an enrollment period of one year and a total study duration of three years. For the primary analysis, the desired detectable hazard ratio for mortality risk is 0.85 comparing the Intervention arm to the Usual Care arm in the primary treatment assessment population. To achieve 80% power with two-sided alpha level of 0.05, the trial requires 402 dialysis facilities (201 in each randomization arm) and a total of 6432 patients (of whom 4020 belong to the primary treatment assessment

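### The revised total sample size is 6,880 in the section 6.2.1 text and both summaries but 6,800 in Table 2R, for the same 4,250 primary-population patients

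*Combined protocol and SAP*

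**What the plan says.** Protocol section 6.2.1 revises the sample size while the trial is under way. Its text states "A sample size of 6,880 (4250 in primary analysis population" and says that this "provides 77 – 82% power to detect a HR of 0.85". The comparison is in the primary treatment assessment population, where "the desired detectable hazard ratio for mortality risk is 0.85 comparing the Intervention arm to the Usual Care arm".

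Table 2R, which that text introduces, has nine rows: the initial design and eight revised scenarios. Four of the revised rows have 4,250 primary-population patients. Each gives a total of 6,800, with power of 80%, 77%, 82% and 80%.

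The Protocol Summary and the summary at the front of the SAP each print "6880 patients". Neither gives a number for the primary population.

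The link between total and primary population comes from section 6.2, which expects an average cluster of 16 patients with about 10 of them in the primary population, printed as 63%.

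**The concern.** A text and the table it summarises should give the same total for the same scenario. Here they do not, and the text's total appears in no row of the table. The total is a headline design figure: it was changed by formal amendment and is repeated in both summaries. Anyone comparing actual with planned enrolment, or reporting the planned size in a results paper, can find two answers in the current text.

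The mismatch also prompts the question whether the power range belongs to one total and not the other. That needs checking, because a power statement attached to the wrong sample size would matter more than a wrong total.

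**Working it through.** **1. Shares and totals**

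- Planning share (section 6.2): 10/16 = 0.625.
- Table 2R, initial design and four revised rows: 4,020/6,432 = 0.625.
- Table 2R, other four revised rows: 4,250/6,800 = 0.625.
- Text pair: 4,250/6,880 = 0.618.
- Total implied by 4,250: 4,250/0.625 = 6,800.
- Primary population implied by 6,880: 6,880 × 0.625 = 4,300.
- Gap: 6,880 − 6,800 = 80 patients; 80/6,800 = 1.2%.

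The other shares in the documents do not lead to 6,880 either. The printed 63% gives 4,250/0.63 = 6,746. The 65% implied by section 6.1 (about 35% above 42.5 L) gives 4,250/0.65 = 6,538. Both lie further from 6,880 than 6,800 does.

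**2. Reproducing the stated power at 4,250**

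Inputs from sections 6.2 and 6.2.1 and Table 2R: HR 0.85 with "power to detect a HR of 0.85 with a two-sided alpha of 0.05"; 1:1 allocation; "a cluster number of 256 and cluster size standard deviation (SD) of 10 or 16"; accrual over 36 of 54 months; ICC 0.015 or 0.012; 10% annual loss; and a mortality source that "suggests an overall mortality rate of 18% per year among incident patients".

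Assumptions: 18% is the annual death probability averaged over the two arms, accrual is uniform, death and loss are exponential, and follow-up runs to month 54.

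- Hazards: death −ln(1 − 0.18) = 0.198 per year (arm average); loss −ln(1 − 0.10) = 0.105 per year.
- Expected deaths: D = N × P(death) = 1,619 at N = 4,250.
- Design effect: DE = 1 + [(1 + CV²)m − 1] × ICC, with m = 4,250/256 = 16.6 and CV = SD/m. For SD 10 and ICC 0.015, CV = 0.602 and DE = 1.324.
- Power (Schoenfeld): Φ(|ln 0.85| × √(D/(4·DE)) − 1.96). For that row: 0.1625 × √(1,619/(4 × 1.324)) − 1.96 = 0.88, so power is 81.1%.

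**3. The same calculation at 4,300**

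Here m = 4,300/256 = 16.8 and D = 1,638.

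| ICC | SD | DE at 4,250 | Table 2R power | Recomputed at 4,250 | Recomputed at 4,300 | Change (points) |
|---|---|---|---|---|---|---|
| 0.015 | 10 | 1.324 | 80% | 81.1% | 81.5% | 0.4 |
| 0.015 | 16 | 1.465 | 77% | 77.1% | 77.5% | 0.4 |
| 0.012 | 10 | 1.260 | 82% | 83.0% | 83.4% | 0.4 |
| 0.012 | 16 | 1.372 | 80% | 79.7% | 80.2% | 0.5 |

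All four stated powers are reproduced to within about 1 point, and the text's 77 to 82% is exactly the range of these four rows. The total sample size does not enter the formula.

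**4. Sensitivity to the assumptions**

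- With 18% as the Usual Care rate, power is 78.8, 74.7, 80.8 and 77.4% at 4,250, and 79.2, 75.1, 81.2 and 77.8% at 4,300.
- With 18% as the arm average and follow-up capped at 3 years, power is 78.3, 74.2, 80.3 and 76.9% at 4,250, and 78.7, 74.6, 80.7 and 77.4% at 4,300.

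The level moves with these choices, but the difference between 4,250 and 4,300 stays at 0.4 to 0.5 points.

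**The case against.** The best defence is that the trial's size is stated consistently wherever it is stated as such: 6,880 in the section 6.2.1 sentence and in both summaries, and the amendment log also records the increase to that figure. The value 6,800 stands only in one column of a scenario table. The primary share is also a planning approximation, and 61.8% is within 0.7 points of 62.5%, so 6,880 with 4,250 is not impossible in itself.

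Much of this stands. It means that 6,880 cannot be called the error, and that the table may be what needs correcting. It does not remove the conflict. The table pairs 4,250 with 6,800 four times, no section states a 61.8% share, and none describes an allowance of 80 patients.

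A reader might also infer that the quoted power belongs to a different sample size from the one stated. The documents do not support that, because the power is for the primary population and the text and table agree on 4,250. Nor do they support the idea that the summaries repeat the mismatched pair, since they print only the total. Finally, one might suppose that enrolment stops at one of two competing counts. No section sets a stop by count: the summaries give a 3-year enrolment period, and section 7.3 expects enrolment to take about that long.

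**Conclusion.** The inconsistency is real and lies in current text: two totals, 80 patients (1.2%) apart, for the same 4,250 primary-population patients. Only 6,800 agrees with the share used throughout Table 2R, but the documents do not establish which total was meant.

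It is an error in a stated design figure, not a shortfall in power. The power range stands as written for 4,250, and if 6,880 implies 4,300 the range shifts up by less than one point. The conclusion on the totals rests on arithmetic alone. The conclusion on power rests on the assumptions listed in the check, and the difference between the two sizes is insensitive to them. No effect follows for alpha, the target hazard ratio or the analysis method. The point deserves correction because the figure is prominent and easy to put right.

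**What to change.** Settle on one total and use it throughout.

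- If 6,800 was intended, change the section 6.2.1 sentence, the Protocol Summary and the SAP summary to 6,800. Table 2R stays as it is.
- If 6,880 was intended with the 62.5% share, change the four affected rows of Table 2R to 4,300 and 6,880, rerun their power with the sponsor's own method, and update the 4,250 and the power range in the sentence. The summaries need no change.
- If 6,880 was intended with 4,250, change the total in those four rows to 6,880 and state the 61.8% share as the assumption. The power figures stay.

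The first and third options are wording only. The second adds a rerun of four table rows. None of them requires a change to the analysis.

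### Table 2's expected deaths do not fall with the hazard ratio: if 18% is the Usual Care rate, the 402-facility design has about 77% power, not 80%, and the current design slightly less than stated

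*Combined protocol and SAP*

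**What the plan says.** Protocol Section 6.2 reports that provider data from January 2011 to May 2012 "suggests an overall mortality rate of 18% per year among incident patients". It adds "Other assumptions include a loss to follow-up rate of 5% per year" and "an ICC for mortality of 0.03 is expected", with about 10 primary-population patients per facility, one year of enrollment and three years in total. "To achieve 80% power with two-sided alpha level of 0.05" at HR 0.85, it asks for 402 facilities and 4,020 patients in the primary population. Table 2 gives sizes for HR 0.90, 0.85 and 0.80 at three ICC values.

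Section 6.2.1 revises this to 256 facilities, cluster-size SD 10 or 16, 36 months of enrollment in a 54-month study, and "a loss to follow-up rate of 10%, and an ICC for mortality of 0.012 or 0.015". Mortality stays at 18% in every row of Table 2R. The four rows with 4,250 primary-population patients show 80, 77, 82 and 80% power, summarised as "4250 in primary analysis population) provides 77 – 82% power to detect a HR of 0.85". SAP Section 3.1 repeats 80% power for HR 0.85 in the plan given to the DSMB.

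Neither document gives the expected number of deaths, the arm to which the 18% applies, or the design-effect formula.

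**The concern.** Power for a survival comparison depends on the number of deaths. If the intervention works as hypothesised, the Intervention arm contributes fewer of them, and the expected count must fall as the assumed effect grows. A calculation that uses one death rate for everyone, whatever the hazard ratio, counts deaths that the alternative hypothesis says will not occur. The effect is modest, but it always favours the design.

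The protocol and the plan sent to the DSMB rest on these power figures. The June 2016 revision updated the ICC, loss to follow-up, cluster count and study length, but not mortality, although about 5,000 enrolled participants had already supplied the observed ICC.

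**Working it through.** **Inputs (protocol Sections 6.2 and 6.2.1).** Annual percentages are converted to hazards by −ln(1 − p).
- Usual Care hazard λ = −ln(0.82) = 0.1985. At HR 0.85 the Intervention hazard is 0.1687, an annual risk of 15.5%.
- Loss hazard η = 0.0513 (5%) or 0.1054 (10%).
- Enrollment A and total duration T are 1 and 3 years, or 3 and 4.5 years.

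**Formulas.** With uniform accrual, the probability of an observed death is

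p = λ/(λ+η) × [1 − (e^(−(λ+η)(T−A)) − e^(−(λ+η)T)) / ((λ+η)A)].

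Power = Φ(|ln HR| × √(D / (4·DE)) − 1.96), where D is deaths and DE the design effect.

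**Step 1: reproduce the 402-facility figure.** DE = 1 + 9 × 0.03 = 1.27. With 18% in both arms p = 0.368, so D = 4,020 × 0.368 ≈ 1,479, or 1,165 after dividing by 1.27. Power is 79.2%, close to the stated 80%. Reading 18% as 18 deaths per 100 person-years gives 76.1% on a common rate, so the risk conversion fits better.

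**Step 2: what death probability does Table 2 imply?** At 80% power the effective deaths needed are 4 × (1.96 + 0.84)² / (ln HR)²: about 2,828, 1,189 and 631 for HR 0.90, 0.85 and 0.80. Multiplying by DE and dividing by the tabulated size gives, at ICC 0.03:
- HR 0.90: 2,828 × 1.27 / 9,700 = 0.370
- HR 0.85: 1,189 × 1.27 / 4,020 = 0.376
- HR 0.80: 631 × 1.27 / 2,160 = 0.371

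All nine rows lie between 0.370 and 0.376. A common 18% predicts 0.368 throughout. A reduced Intervention hazard predicts 0.353, 0.346 and 0.338, and Table 2 would then need about 5, 8 and 10% more patients.

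**Step 3: 402 facilities with the Intervention hazard reduced.** Usual Care: 2,010 × 0.368 ≈ 739 deaths. Intervention: 2,010 × 0.3235 ≈ 650. The total is about 1,390, against 1,189 × 1.27 ≈ 1,510 needed for 80%. Effective deaths are 1,390 / 1.27 ≈ 1,094, and power is 76.7%.

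**Step 4: current design, 4,250 patients.** Mean cluster size m = 4,250 / 256 = 16.6. A common 18% gives p = 0.381 and about 1,621 deaths. The reduced hazard gives 811 + 717, about 1,527 deaths. Two design effects are used:
- CV-based: 1 + ((1 + CV²)m − 1) × ICC.
- Efficient weighting: a cluster of size n counts as n / (1 + (n − 1) × ICC). Gamma-distributed sizes are an assumption made here.

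| SD, ICC | Stated power | CV-based DE | Common 18% | Reduced | Efficient DE | Common 18% | Reduced |
|---|---|---|---|---|---|---|---|
| 10, 0.015 | 80 | 1.324 | 81.1 | 78.8 | 1.303 | 81.8 | 79.4 |
| 16, 0.015 | 77 | 1.465 | 77.1 | 74.7 | 1.403 | 78.9 | 76.5 |
| 10, 0.012 | 82 | 1.260 | 83.0 | 80.8 | 1.245 | 83.5 | 81.2 |
| 16, 0.012 | 80 | 1.372 | 79.8 | 77.4 | 1.329 | 81.0 | 78.7 |

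Reducing the Intervention deaths costs about 2.2 to 2.4 points under either formula. Against the stated values, the reduced figures are 1.2 to 2.6 points low with the CV-based formula and 0.5 to 1.3 points low with efficient weighting.

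**The case against.** **The 18% could be a two-arm average.** Section 6.2 calls it an overall rate and assigns it to no arm. Read as the average of the two hazards (about 19.3% Usual Care and 16.7% Intervention at HR 0.85), it reproduces the plan equally well: 79.1% for 402 facilities, and Table 2 within 2.2%. On that reading there is no arithmetic error. The objection stands in that the cause is an inference. But the 18% was observed before any facility received the intervention. The average reading would also need a Usual Care rate of about 18.9, 19.3 and 19.8% as the assumed HR moves from 0.90 to 0.80. The protocol states none of these, and a control rate should not rise with the effect hypothesised.

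**Table 2R does not show which count was used.** With the CV-based formula the common-rate count fits the 4,250-patient rows within 1.1 points; with efficient weighting the reduced count fits within 1.3. The choice is open: protocol Section 6.3 specifies a robust variance and SAP Section 4.3 a frailty model, which weights unequal clusters more efficiently. This stands, and it limits the claim for the current design.

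**Other inputs could offset the shortfall.** Section 6.2.1 reports an observed ICC near 0.01. At that value the reduced count with the CV-based formula gives 82.1% (SD 10) and 79.2% (SD 16). Section 1.1 says that smaller patients survive less well. With an assumed 20% in Usual Care, the reduced calculation gives 80.3% for 402 facilities and 78.2 to 84.0% for the current rows. This is fair, and it argues for using the observed death rate rather than for leaving 18% unexplained.

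**Conclusion.** The point holds for Table 2 and the 402-facility row. The tabulated sizes imply a death probability that does not respond to the hazard ratio. With 18% as the Usual Care rate, power is about 77% rather than 80%. Equal clusters are assumed there (Table 2R lists SD 0), so that figure does not depend on how unequal clusters are handled. It does rest on reading 18% as a Usual Care annual risk, constant hazards and uniform accrual.

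For the current design the overstatement is smaller: about 1 to 3 points or about 0.5 to 1.3 points, depending on the design-effect formula.

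A reader might infer that the trial's power is established as 75 to 81% in place of 77 to 82%. The documents do not support that: the lower range follows from one unstated formula, and the other gives about 76 to 81%. A reader might also take the common rate in both arms as a documented fact. It is the best reading of Table 2, not something that the protocol says.

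**What to change.** 1. In Section 6.2, state which arm or arms the 18% describes and give the expected deaths per arm.
2. Recompute Tables 2 and 2R with the Intervention hazard set to HR times the Usual Care hazard, and name the design-effect formula for unequal clusters.
3. Add a Table 2R row at the death rate observed, pooled over arms, in the participants who supplied the ICC. A pooled rate reveals nothing by arm.
4. Restate the power for 402 facilities (about 77% if 18% is the Usual Care rate) and replace the range in Section 6.2.1 with the recomputed one.
5. Leave SAP Section 3.1 as the record of what the DSMB received, with a note giving the recomputed power.

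The work is a recalculation and a few text edits. No patients are added and no analysis changes. The cost is a slightly less favourable stated power.

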#### Table 2R. Revised Sample Size Requirement

#### 6.3. Statistical Analyses

In addition to the analyses described in this section, descriptive statistics will be used during the conduct of the trial as part of data management plan for monitoring data quality. An overview of the statistical methods used both for descriptive purposes and in analyses of the primary research questions, is summarized in the following sections. More comprehensive plans for data management and statistical analyses will be provided as formal Data Management and Statistical Analysis Plans.

#### **Descriptive Analyses**

Standard descriptive statistics will be used to summarize baseline characteristics and study outcome measures at each follow-up visit, both overall, and within each treatment arm. Summary statistics such as means, medians, and ranges will be produced for all continuous variables. Frequencies will be computed for all categorical and ordinal variables. Graphical methods including histograms, stem-and-leaf diagrams and boxplots will be used to examine distributions, identify potential influential points, and guide in the choice of transformations, if warranted. The balance of baseline measures across the two treatment arms will be compared with robust variance estimate to take in account the clustering effect.

